10.1.4 Clinical Laboratory Changes

Changes in laboratory values, vital signs or other safety parameters (e.g., neurological and clinical symptom assessments) as noted in the protocol are a subset of Aes and are reportable only if the lab test result is associated with accompanying symptoms, and/or requires additional diagnostic testing or intervention (medical, surgical), and/or requires additional significant

treatment, and/or requires temporal or permanent discontinuation of IMP, or a change to dosing other than as permitted by protocol, or if considered to be clinically significant by the Investigator or medically qualified designee.

Screening laboratory assessments, if determined to be clinically significant by the Investigator, are not Aes.

It is noted that any liver abnormality $> 3x$ ULN should be carefully assessed by the Investigator to determine whether it should be considered an AE. Guidance for the procedures to follow for elevated liver function tests are provided in [Appendix 3](#).

11 SERIOUS ADVERSE EVENTS

The Investigator or designee is responsible for identifying, documenting and reporting events that meet the definition of an SAE.

An SAE is any event that meets any of the following criteria:

- Death
- Life-threatening
- Inpatient hospitalization or prolongation of existing hospitalization
- Persistent or significant disability/incapacity
- Congenital anomaly/birth defect in the offspring of a subject who received SUBLOCADE injection
- Other: Important medical events that may not result in death, be life-threatening, or require hospitalization, may be considered an SAE when, based upon appropriate medical judgment, they may jeopardize the subject and may require medical or surgical intervention to prevent one of the outcomes listed in this definition. Examples of such events are:
 - Intensive treatment in an emergency room or at home for allergic bronchospasm
 - Blood dyscrasias or convulsions that do not result in inpatient hospitalization
- Potential Hy's Law cases indicative of medication-induced hepatocellular injury, defined as:
 - ALT or AST >3x ULN and total bilirubin of >2x ULN (or INR >1.5 if measured) with no other reason found to explain combination of increased ALT and total bilirubin, such as hepatitis A, B, or C; pre-existing or acute liver disease; or another drug capable of causing the observed injury. Note: INR threshold does not apply to subjects receiving anticoagulants
 - ALT or AST >3x ULN with systemic symptoms (fatigue, nausea, vomiting, right upper quadrant pain or tenderness, fever, rash and/or eosinophilia [> 5%])

Potential Hy's Law cases should be managed as described in Appendix 3.

An AE is considered "life threatening" if the subject was at immediate risk of death from the event as it occurred; i.e., it does not include a reaction that if it had occurred in a more serious form might have caused death. For example, IMP-induced hepatitis that resolved without evidence of hepatic failure would not be considered life threatening even though IMP-induced hepatitis can be fatal.

Adverse events requiring hospitalization should be considered SAEs. Hospitalization for elective surgery or routine clinical procedures that are not the result of AE (e.g., elective surgery for a pre-existing condition that has not worsened) should not be considered AEs or SAEs. If anything untoward is reported during the procedure, that occurrence must be reported as an AE (either ‘serious’ or ‘non-serious’) according to the usual criteria.

In general, hospitalization signifies that the subject has been detained (usually involving at least an overnight stay) at the hospital or emergency ward for observation and/or treatment that would not have been appropriate in the physician’s office or other outpatient setting. Complications that occur during hospitalization are AEs. If a complication prolongs hospitalization or fulfills any other serious criteria, the event is serious. When in doubt as to whether ‘hospitalization’ occurred or was necessary, the AE should be considered serious.

An AE is incapacitating or disabling if the experience results in a substantial and/or permanent disruption of the subject’s ability to carry out normal life functions.

11.1 Documenting Serious Adverse Events

When an SAE occurs, it is the responsibility of the Investigator to review all documentation (e.g., hospital progress notes, laboratory and diagnostic reports) pertaining to the event. The Investigator will then record all relevant information regarding an SAE on the appropriate electronic form in the eCRF.

It is not acceptable for the Investigator to send photocopies of the subject’s medical records to Indivior in lieu of completion of the SAE Reporting Form. However, there may be cases where copies of medical records are requested by Indivior or designated representative. In this instance, all subject identifiers, with the exception of subject number, will be redacted on the copies of the medical records prior to submission to Indivior.

The Investigator will attempt to establish a diagnosis of the event based on signs, symptoms, and/or other clinical information. In such cases, the diagnosis will be documented as an AE or SAE and not the individual signs/symptoms.

11.2 Reporting Serious Adverse Events

11.2.1 Reporting of Serious Adverse Events

Once the Investigator determines that an event meets the protocol definition of an SAE, the SAE will be reported to the IRB by the Investigator (or designee) **within 24 hours** from first being aware of the event by completing the appropriate eCRF(s). Any follow-up information on a previously reported SAE will also be reported to the IRB within 24 hours.

Where additional information is needed or expected, the Investigator will not wait to receive all information before reporting the event to the IRB. The Investigator must provide an assessment of causality at the time of the initial report as described in Section 10.1.3 of the protocol.

Indivior will be informed of SAEs within 24 hours of from the Investigator first becoming aware of the event by using the form provided by Indivior. Any follow-up information on a previously

reporting SAE will be reported to Indivior within 24 hours of the Investigator becoming aware of the update.

Reporting email address: [contact]

11.2.2 Regulatory Reporting Requirements for Serious Adverse Events

Prompt receipt of notifications of SAEs to the IRB or designated representative from investigators is essential in ensuring that legal obligations and ethical responsibilities regarding the safety of subjects are met.

A suspected unexpected serious adverse reaction (SUSAR) is an SAE related to the IMP administered in any dose and that, in its nature or severity, is inconsistent with the IB or Product Information for marketed products.

11.2.3 Overdose

Any instance of intentional OD (whether or not it involved IMP) must be communicated as an SAE and fully documented. Details of any signs or symptoms and their management should be recorded, including details of any antidote(s) administered.

11.2.4 Depot removal

Any instance of depot removal (by a clinician, or injection site tampering by the study subject resulting in removal of the depot) will be considered as an AE of special interest and must be communicated to Indivior or designated pharmacovigilance (PV) representative (email address for reporting: [contact]) within 24 hours of the Investigator first becoming aware of the event by using the SAE reporting form provided by the Indivior (seriousness criteria to be left unticked, if applicable).

12 PREGNANCY

12.1 Collecting and Reporting Pregnancy Information

All pregnancies will be collected from receipt of IMP through the scheduled 30-day follow-up phone call. Subjects who do not continue in MAT will have pregnancies collected until 5 terminal half-lives following the last dose of IMP. For this IMP this period is approximately 12 months. All confirmed pregnancies that occur within this study will be followed until resolution (i.e., termination [voluntary or spontaneous] or birth).

Pregnancy of a study subject without associated unexpected or adverse sequelae is not a reportable AE, but must be reported to Indivior or designated PV representative (email address for reporting: [contact]), using the Clinical Trial Pregnancy Reporting Form within 24 hours of the Investigator first being aware of the pregnancy.

The pregnancy must be followed up to determine outcome (including premature termination) and status of mother and infant. Generally, follow-up will not be required for longer than 6 to 8 weeks beyond the estimated delivery date; however, additional follow-up for up to 2 years may be required if there are any complications for the infant. Any termination of pregnancy will be reported, regardless of foetal status (presence or absence of anomalies) or indication for procedure.

Any pregnancy complication or elective termination for medical reasons must be reported as an AE or SAE. Any SAE occurring in association with a pregnancy, brought to the investigator's attention after the subject has completed the study and considered by the Investigator as possibly related to the study treatment, must be promptly reported to Indivior or designated PV representative. While the Investigator is not obligated to actively seek this information in former study subjects, he or she may learn of an SAE through spontaneous reporting.

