Once subjects are engaged in care at the treatment clinic, they will continue to receive SUBLOCADE for 6 months. The second 300 mg injection will be administered on Day 8 (-0/+4 days) after the first injection, with subsequent 300 mg injections administered at 28-day (-2/+4 days) intervals over approximately 6 months for a total of 7 injections. If necessary, for tolerability, the dose of SUBLOCADE can be reduced to 100 mg. All subjects will receive site standard psychosocial therapy at least weekly during the first 3 months of treatment, and twice monthly thereafter if clinically stable.

All subjects will complete an End of Treatment (EOT) / Early Termination (ET) visit 28 days after their last injection of SUBLOCADE. Within 3 months prior to or at the EOT visit, the Investigator or a medically qualified sub-investigator will discuss the subject's available treatment options and arrange referral. All subjects will receive a safety follow-up telephone call, 30 days after their EOT/ET visit to assess AEs, SAEs, pregnancy status (if applicable) and concomitant medications. Subjects who decline to continue in medication assisted treatment (MAT) will receive monthly safety follow-up phone calls for an additional 5 months (6 months total) to assess SAEs, pregnancy status (if applicable) and concomitant medications.

Primary Endpoint(s):

The primary endpoint of this study is:

- Time to repeat OD or opioid-related death. Repeat OD or opioid-related death will be measured from electronic medical records and state death registries.
- Additional comparisons on repeat OD and death rates will be made to concurrent patients who decline to participate in the SUBLOCADE injection.

Secondary Endpoint(s):

The key secondary endpoint of the study is:

- Treatment engagement as measured by attending the outpatient clinic and receiving subsequent buprenorphine treatment at 3 and 6 months.

The secondary endpoints of this study are:

- Numbers and percent of subjects in treatment at 3 and 6 months after opioid OD.

Exploratory Endpoints:

The exploratory endpoints of this study are:

- Opioid craving in subjects as measured by Craving Visual Analog Scale (VAS) scores.
- Illicit opioid use as measured by urine drug screen (UDS) results.
- Genetic predictors of treatment response and OD.

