4 STUDY PLAN

4.1 Study Design

4.2 Duration of Treatment

The total duration of study participation will be approximately 7 months. Subjects will be treated for 6 months with an End of Treatment (EOT) visit at 7 months.

Safety follow-up telephone calls will occur 30 days after the EOT Visit if the subject is continuing in treatment, with an additional 5 monthly phone calls (6 months total) if the subject is not continuing in MAT.

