12.2 Action to be Taken if Pregnancy Occurs in a Female Subject

If a female subject suspects that she is pregnant (e.g., missed period, self-administered pregnancy test) during treatment or within 6 months after the discontinuation of SUBLOCADE, she should return to the clinic as soon as possible to undergo a urine pregnancy test. Subjects will receive a card with clinic information at the screening visit, including instructions on follow-up should they suspect pregnancy (follow up with the clinic or their usual place of care).

If pregnancy is confirmed at any time during the study, the subject will be withdrawn from study treatment and will undergo all final study visit procedures (with the exception of any additional pregnancy testing) and continue with monthly telephone follow-up. Subjects who are determined to be pregnant will be referred to the VCU outpatient obstetrics clinic or other obstetrics clinic in the local vicinity if they do not wish to attend the VCU clinic.

The Investigator should fully inform the female subject of the potential risk to the fetus as well as discuss the desirability of continuing the pregnancy.

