14.9.2 Extent of Exposure

The duration of treatment with SUBLOCADE, defined as the date of the last injection minus the date of first injection +28 days, will be summarized as a continuous summary.

The total number of SUBLOCADE injections will be presented as a continuous summary and a categorical summary. The number of subjects who had early surgical removal of SUBLOCADE depot will be summarized.

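### For women not continuing in MAT, the 12-month pregnancy collection period in 12.1 runs roughly 4 to 5.4 months past both the 12.2 return instruction and a completer's last scheduled call

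*Combined protocol and SAP*

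**What the plan says.** **Collection period.** Section 12.1 sets two rules. Pregnancies are collected through the 30-day call in general. For the others it says: "Subjects who do not continue in MAT will have pregnancies collected until 5 terminal half-lives following the last dose of IMP". It then gives the length: "For this IMP this period is approximately 12 months".

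**Scheduled contact.** Under the Synopsis (Study Design), the end-of-treatment or early-termination (EOT/ET) visit is a "visit 28 days after their last injection of SUBLOCADE". A safety call follows 30 days later. Subjects who decline further MAT receive monthly calls "for an additional 5 months (6 months total) to assess SAEs, pregnancy status (if applicable) and concomitant medications". Section 4.2 agrees: "with an additional 5 monthly phone calls (6 months total) if the subject is not continuing in MAT". Appendix 2 puts the seventh injection on Day 148, EOT on Day 169 and the 30-day call on Day 199.

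**Return instruction.** Section 12.2 asks a woman who suspects pregnancy "during treatment or within 6 months after the discontinuation of SUBLOCADE" to return for a urine test. It also provides a card at screening with "instructions on follow-up should they suspect pregnancy (follow up with the clinic or their usual place of care"). No time limit is given for the card, and its text is not in the documents.

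**Disposition of pregnant subjects.** Section 6.4.2 describes a subject who has stopped both treatment and the monthly calls as withdrawn from the study, then says that women with confirmed pregnancies will be withdrawn from the study, and refers to 12.2. Section 12.2 withdraws them from study treatment and keeps the monthly calls going.

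**The concern.** The 12-month period in 12.1 is tied to drug exposure: five half-lives of a depot product. Sites can fill that period only through contacts they initiate or through women who know to report. Both stop well short of it. A woman who becomes pregnant in month 9 after her last injection is inside the collection period, but nobody is scheduled to ask her and the only dated instruction she has been given has lapsed.

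What is at stake is detection. Once a pregnancy is known, 12.1 has confirmed pregnancies within the study followed to resolution. If few or none were reported from the last months of the period, the reader could not tell whether none occurred or none were heard of.

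**Working it through.** **Inputs**
- Collection period: about 12 months after the last dose (12.1), taken as 365 days. The documents give no half-life, so the 12-month figure cannot be recomputed; it implies 365 / 5 = 73 days per half-life.
- Seventh and last injection: Day 148 (Appendix 2). This agrees with the dosing rule: Days 1 and 8, then every 28 days, so 8 + 5 × 28 = 148.
- EOT: Day 169 in Appendix 2 (21 days after Day 148); 28 days after the last injection in the Synopsis; or about 7 months in 4.2 and the Synopsis.
- Calls: 30 days after EOT, then five more at monthly intervals. Five months is 150 days with 30-day months, or 152 with calendar months (30.44 days).

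**Step 1: last pregnancy-status call, completer not continuing in MAT**

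Days from last injection to last call = (EOT − last injection) + 30 + five months.

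| Reading of EOT | Calculation | Days | Months | Left of 365 days |
|---|---|---|---|---|
| Appendix 2, Day 169 | 21 + 30 + 150 | 201 | 6.6 | 164 (5.4 months) |
| 28 days after last injection | 28 + 30 + 150 | 208 | 6.8 | 157 (5.2 months) |
| Same, calendar months | 28 + 30 + 152 | 210 | 6.9 | 155 (5.1 months) |
| EOT literally at 7 months (Day 213) | 65 + 30 + 150 | 245 | 8.0 | 120 (3.9 months) |
| Same, calendar months | 65 + 30 + 152 | 247 | 8.1 | 118 (3.9 months) |

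The first three rows follow the protocol's specific timing rules. The last two rest on its looser statement that EOT is at 7 months. In half-lives, the first three rows reach 201 / 73 = 2.8 to 210 / 73 = 2.9 of the five.

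**Step 2: the 12.2 instruction**

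Six months is 183 days.
- If discontinuation means the last injection, the instruction lapses at day 183 and falls 365 − 183 = 182 days short.
- If it is counted from 28 days later, by analogy with the treatment duration in 14.9.2 ("defined as the date of the last injection minus the date of first injection +28 days"), it lapses at 183 + 28 = 211 and falls 365 − 211 = 154 days short.

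**Step 3: calls and instruction together**

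Cover ends at whichever comes later.
- Appendix 2 or the 28-day rule: cover ends between day 201 and day 211, leaving 164 down to 154 days (5.4 to 5.1 months).
- Month-7 reading of EOT: cover ends at day 245 to 247, leaving 120 to 118 days (about 4 months).

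Every reading falls short of 12 months. The uncovered stretch is roughly 4 to 5.4 months.

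**Step 4: 6.4.2 against 12.2**

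No arithmetic applies. Taken with its own description of study withdrawal, 6.4.2 implies that a pregnant subject's calls stop. Section 12.2 says they continue. Since 6.4.2 sends the reader to 12.2, the more specific rule is evidently the intended one.

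**The case against.** The strongest reply is that nothing here is contradictory. Section 12.1 says how long pregnancies are collected, without saying that collection is active or by telephone. Its reporting clock starts when the investigator becomes aware, which suits passive reports, and the card has no stated end date. A long passive period beside a shorter call schedule can be followed as written, and the 6 months in 12.2 concerns a clinic test, not recording.

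Part of this stands. A reader might infer that the protocol contradicts itself, or that pregnancies after the last call will be missed. The documents support neither: late reports would still be collected, and the unseen card may already cover 12 months. But passive collection depends on women knowing to report. The only instruction with a date ends at 6 months, and no 12-month instruction appears anywhere in the documents.

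Section 12.1 also says the investigator need not actively seek certain information in former subjects. That sentence concerns serious adverse events associated with a pregnancy; it does not shorten the collection period.

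The figures are also less tight than 201 to 210 days suggests, because the month-7 wording moves the last call to about 8 months. That is why the range is given as 4 to 5.4 months. The table of contents still labels Appendix 2 as running to Day 381, which may be leftover text; 381 − 148 = 233 days would leave 365 − 233 = 132, inside the same range.

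The figures are for completers. Section 6.4.1 keeps most early discontinuers on monthly calls through their scheduled 30-day call, but it is unclear how that span is counted and pregnancy is not among the stated purposes of those calls. No figure is offered for them.

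**Conclusion.** The mismatch is real and minor. For women of child-bearing potential who complete treatment and do not continue in MAT, about 4 to 5.4 months of the period set in 12.1 have neither a scheduled contact nor a stated instruction to return. The size rests on three assumptions: approximately 12 months means 365 days; the last dose is the Day 148 injection; and the card says no more than 12.2 does. How many of the approximately 100 subjects are affected is not stated. Women who continue in MAT are outside the point, because their collection ends at the 30-day call.

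Two stronger inferences should be resisted. One is that the call schedule must be extended. The documents do not show whether the 12-month period or the 6-month schedule better reflects the sponsor's intent, and added calls are a resource choice. The other is that 6.4.2 drops pregnant women from follow-up and so distorts the primary endpoint. Its cross-reference to 12.2 settles the rule, and 14.7.1 also tracks events through medical records and death registries. There is no effect on the primary endpoint, power or sample size.

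**What to change.** 1. In 12.2 and on the screening card, replace "during treatment or within 6 months after the discontinuation of SUBLOCADE" with: during treatment or within 12 months after the last dose of SUBLOCADE. This matches 12.1 and removes the doubt about what counts as discontinuation. It should apply to all women, as the present instruction does, because the card is issued before anyone knows who will continue in MAT. The cost is a wording change, plus a few more urine pregnancy tests and reports.
2. In 6.4.2, say that pregnant subjects are withdrawn from study treatment, with monthly telephone follow-up continuing per Section 12.2. This is wording only.

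Optional for the sponsor: monthly pregnancy-status calls to about 12 months after the last dose. Under the Appendix 2 or 28-day timing this means about 5 to 6 more calls per affected completer (155 / 30 = 5.2 to 164 / 30 = 5.5). Item 1 does not depend on it.

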12.2 Action to be Taken if Pregnancy Occurs in a Female Subject

If a female subject suspects that she is pregnant (e.g., missed period, self-administered pregnancy test) during treatment or within 6 months after the discontinuation of SUBLOCADE, she should return to the clinic as soon as possible to undergo a urine pregnancy test. Subjects will receive a card with clinic information at the screening visit, including instructions on follow-up should they suspect pregnancy (follow up with the clinic or their usual place of care).

If pregnancy is confirmed at any time during the study, the subject will be withdrawn from study treatment and will undergo all final study visit procedures (with the exception of any additional pregnancy testing) and continue with monthly telephone follow-up. Subjects who are determined to be pregnant will be referred to the VCU outpatient obstetrics clinic or other obstetrics clinic in the local vicinity if they do not wish to attend the VCU clinic.

The Investigator should fully inform the female subject of the potential risk to the fetus as well as discuss the desirability of continuing the pregnancy.

